2.1 Sample Size

A power calculation could not be performed because this is an exploratory study. The technology is still under development and the clinical utility and potential applications are uncertain. Based on prior studies showing equivalence between PCCT and conventional CT images performed in normal volunteers, patient in various disease states will be studied.

3. Aims and Objectives

To perform imaging with the prototype scanner on patients with clinical diseases to evaluate image quality.

4. Outcomes

4.1 Primary outcome

Mean difference in relative image quality grading of CT images using Photon counting detectors compared to conventional detectors in group of patients with various clinical conditions.

4.2 Safety Outcomes

Adverse events related to the scanner are not anticipated but will be reported as outlined in the protocol.

5.0 Populations and subgroups

5.1 Population

All enrolled participants who complete the PCCT scan.

5.2 Subgroups

Potential subgroups will be established if sufficient number of patients with specific diagnoses are accrued.

6.0 Analysis

6.1 Primary Outcome

Mean difference in relative image quality grading of CT images using Photon counting detectors vs. conventional detectors in group of patients with various clinical conditions.

Expert radiologist observers compare the relative grading of the images from the PCCT to the grading of the same patient's reference images from conventional CT acquired at the same time. They will use the method termed "Visual grading analysis (VGA)". The visual grading scale incorporates technical factors in the acquisition and image display (such as contrast, noise and presence of artifacts and post processing). Grading is based on 5-point scale. 1- lowest image quality, 5- highest image quality. 5 is a better result. Scale as follows: 1 Images not usable- severe limitations for diagnostic use, 2 Limited -some loss of information, significant limitations for clinical use, 3 Adequate -moderate limitations for diagnostic use, 4 Good-minimal limitations for clinical use, 5 Excellent- no limitations for clinical diagnosis.

The mean difference and standard deviation of the group will be reported.

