As a translational development protocol, all imaging studies are open-label and data may be analyzed as they are collected. Bias is minimized using objective measurements. Observational data may be characterized using descriptive statistics. Simple comparisons between the standard CT and PCCT may use paired and unpaired parametric and non-parametric techniques. These studies will form the foundation to develop advanced clinical imaging capabilities and applications.

1. Introduction, Background and Rationale

The NIH intramural program specifically includes developing novel imaging techniques as one of its priorities for accelerating science, including generating new methodologies for non-invasive patient assessments (<https://irp.nih.gov/our-research/accelerating-science/developing-novel-imaging-techniques>). Computed tomography (CT) is a core imaging modality in medicine. In CT imaging, an X-ray tube and an X-ray detector are rotated around the patient with the detector recording X-ray penetration continuously during exposure. That data is then used to reconstruct cross-sectional images of the patient for diagnostic purposes. There are myriad ways to structure the examination of a body area, e.g. the system settings for the X-ray exposure, data collection and reconstruction and display of the images. Typical, optimized exam protocols have been developed for CT imaging for each area of the body and each organ as well as unique aspects of physiology, allowing for visualizing differences between normal and abnormal tissues and function.

The current clinical CT scanners at the NIH/RAD&IS have dual source capability with two X-ray tube/detector pairs that rotate around the patient simultaneously. Dual-source CT can be used to double the speed of acquisition or to perform dual energy scanning that may aid in determining tissue composition. These traditional CT systems detect X-rays using scintillator crystals and a photodiode array in an energy-integrating detector (EID) system that measures the total X-rays that pass through the patient and reach the detector. In these detectors, the individual imaging elements are separated by metal septae that limit the achievable spatial resolution.

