Because this is a translational development protocol for new technology, all imaging procedures are open-label and data may be analyzed as they are collected. Bias is minimized by defining and using objective measurements and recording them for review. Observational data may be characterized using descriptive statistics. Simple comparisons between the standard and PCCT images may use paired and unpaired parametric and non-parametric techniques as appropriate. New methods may be compared to the standard CT or computational models of the imaging studies. Objective quantitative measurements used in CT performance include, but are not limited to noise level and standard deviation, signal to noise ratio and variance, radiation dose and qualitative measures such as radiologist ratings of image quality, lesion conspicuity, image noise, beam hardening artifact, motion artifact.

3. Study Design and Methods

NIH patients referred to RAD&IS for diagnostic CT may be approached for participation in the study of PCCT-The study team has shared information about the PCCT study with NIH researchers that frequently schedule their patients for diagnostic CT scans as part of their studies. Those researchers or other NIH research teams may refer patients for study participation in this PCCT study. Enrolled patients will undergo the requested clinical diagnostic CT study on the PCCT system using the standard detector, with or without IV and/or oral contrast as indicated for the diagnostic CT scan. If contrast is not indicated for the diagnostic scan, it will not be administered for the research PCCT study. They will also undergo a brief PCCT scan as part of the examination. The standard detector and PCCT scans may be performed in any order. The scan will thus include both clinically indicated radiation exposure with the standard detector and research radiation with the PCCT detector.

From the patient perspective, the experience is the same as with a standard CT study. The CT scans are accomplished by having the subject lie down on a patient table which slides into the gantry of the scanner, a hollow cylinder 78 cm in diameter. The scan is performed by a qualified person in an adjacent room; audible communication is by intercom. In addition, the patient can be observed directly through the window between the two rooms. The patient can be removed from the scanner immediately upon request or in case of emergency.

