7.2. Analysis of Study

Each patient will undergo a CT scan using the standard detector that will be submitted to the Radiology & Imaging Sciences Department for interpretation.

The PCCT scan will cover either identical volumes or, in many cases, a smaller volume. Often the smaller volume will be selected for study rather than the full clinically indicated body part(s) included in the standard detector scan. This allows direct comparison between the scans for image assessment. Objective quantitative measurements will include but are not limited to image noise level and standard deviation, signal to noise ratio and variance, radiation dose and qualitative measures such as radiologist's ratings of image quality, lesion conspicuity, image noise, beam hardening artifact, motion artifact. Comparisons of these quantitative and qualitative measures in different PCCT protocols among similar patients may also be made. As observational experience is gained with PCCT capabilities, the data will be used to generate hypotheses that may be investigated by future amendments, future cohorts, or future protocols. Because this is a translational development protocol for new technology, all imaging procedures are open-label and data may be analyzed as they are collected.

This protocol provides data for technical development purposes. The results may be used to iteratively improve the PCCT software and hardware for application to patient care. The relationship with the industry partner (Siemens Medical Solutions) is governed by an approved and active NIH CRADA. The CRADA document is available for IRB Chair review, upon request.

8. Data Safety and Monitoring Plan

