8.1. Data and Safety Monitoring

Accrual and safety data will be monitored by the principal investigator, who will provide oversight to the conduct of this study. The PI will continuously evaluate implementation of the protocol for any unusual or unpredicted complications that occur and will review the data for accuracy and completeness.

The NIH Clinical Center's Quality Assurance Program will conduct study monitoring at least annually or more frequently as required for open studies unless studies are monitored by an outside organization or sponsor. Monitoring visits will include a review of patient consent documents, primary outcome and safety laboratory results and diagnostic test results will be monitored for accuracy, correct dating, and agreement between case report forms and source documents. All regulatory reports, reviews and amendments, adverse events and problem reports related to study, along with investigator credentials, training records, and the delegation of responsibility log will also be reviewed during monitoring visits. Any major findings will be summarized in writing and reported to the study PI who will be responsible for submitting the monitoring report to the IRB.

Monitoring will not apply to imaging data measurement, analysis and interpretation. An independent audit of these data is not planned.

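### The SAP's only non-safety outcome is a radiologist's 1-5 image grade with no masked or random-order reading planned, so if readers are unmasked the reported mean difference may mix reader expectation with detector effect

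*SAP*

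**What the plan says.** SAP 4.1 defines the primary outcome as "Mean difference in relative image quality grading of CT images using Photon counting detectors compared to conventional detectors in group of patients" with various conditions. The only other outcome, in SAP 4.2, is safety. SAP 6.1 describes the reading: "Expert radiologist observers compare the relative grading of the images from the PCCT to the grading of the same" patient's conventional images, which it calls reference images, on a 5-point visual grading scale. Noise appears there only as one factor inside the grade. The planned summary is brief: "The mean difference and standard deviation of the group will be reported".

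SAP section 2 has experienced radiologists review the PCCT images on clinical workstations under ordinary reading conditions. Neither document states whether detector labels are visible, whether series are coded for reading, in what order they are read, or whether the two series are seen together or apart.

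The protocol's stated bias control is objective measurement. The Precis says "Bias is minimized using objective measurements", and section 2 says "Bias is minimized by defining and using objective measurements and recording them for review". Section 7.2 adds: "Objective quantitative measurements will include but are not limited to image noise level and standard deviation, signal to noise ratio and variance, radiation dose". The same sentence goes on to list radiologist ratings. Section 7.2 also says: "The PCCT scan will cover either identical volumes or, in many cases, a smaller volume". Sections 2 and 7.2 call the imaging procedures open-label.

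On oversight, protocol 8.1 has the principal investigator review the data for accuracy and completeness, but also says: "Monitoring will not apply to imaging data measurement, analysis and interpretation. An independent audit of these data is not planned".

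**The concern.** A visual grade is a judgement, and knowing which detector produced an image can move it. The protocol gives a reader grounds for expecting a direction. Its Precis lists lower noise and greater resolution as PCCT advantages, and section 9.1 describes head, chest and head-and-neck studies favouring PCCT. Other text points to no difference: the abdominal study in section 9.1 found none of statistical significance, and SAP 2.1 speaks of equivalence. So neither the presence nor the direction of a shift can be assumed.

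The plan as written allows label-aware grading, and the measurements that do not depend on a reader's opinion are not among the SAP outcomes. The resulting estimate has uses. SAP section 1 gives hypothesis generation and feedback to the manufacturer as the aim, protocol 7.2 says results may guide software and hardware changes, and protocol 6.6 says a results summary will be posted.

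**Working it through.** **Inputs.** The documents give no expected grade difference, no SD of paired differences and no estimate of reader effect, so there is no planned figure for the outcome to reproduce. The only relevant number is the ceiling of 750 subjects in protocol 7.1. It equals 150 per year × 5 years = 750, using the accrual figures there, although the protocol does not say it was derived that way. Every share used below is an assumption.

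**Step 1: the mean.** Let d be the average detector effect on the PCCT-minus-conventional grade and b the average expectation shift. Apart from the limits of the scale, the reported mean estimates d + b. A reported mean of 0.20 fits each of these:

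- d = 0.20, b = 0
- d = 0, b = 0.20
- d = 0.30, b = −0.10

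More patients do not shrink b.

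**Step 2: the SD.** Suppose a share p of pairs is graded one point higher for PCCT and the rest tie. Then mean = p and SD = √(p(1−p)).

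| p | mean | SD |
|---|---|---|
| 0.10 | 0.10 | √0.09 = 0.300 |
| 0.20 | 0.20 | √0.16 = 0.400 |
| 0.30 | 0.30 | √0.21 = 0.458 |

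The figures are the same whether the extra points come from the detector, the reader, or half from each, provided no pair receives both effects.

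**Step 3: relaxing that proviso.** If detector and reader each act independently on p/2 of pairs, the mean is still p but SD = √(p(1−p/2)): 0.308, 0.424 and 0.505 for the three values of p. The SD therefore depends on overlap, but this does not identify the source. At p = 0.20 the independent case puts 0.1 × 0.1 = 0.01 of pairs at +2, 2 × 0.1 × 0.9 = 0.18 at +1 and 0.81 at 0. The mean is 0.18 + 0.02 = 0.20, and the SD is √(0.18 + 0.04 − 0.04) = √0.18 = 0.424. A detector acting alone could produce exactly that distribution.

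**Step 4: limits of the scale.** If an assumed share c of PCCT images would already be graded 5, an upward shift falls to p(1−c).

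| p | c = 0 | c = 0.25 | c = 0.50 |
|---|---|---|---|
| 0.10 | 0.100 | 0.075 | 0.050 |
| 0.20 | 0.200 | 0.150 | 0.100 |
| 0.30 | 0.300 | 0.225 | 0.150 |

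The range is +0.05 to +0.30. A downward shift mirrors this, with the limit at grade 1.

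**Step 5: simulation.** Paired grades were drawn from an assumed latent quality (mean 3.8, SD 0.6, reading error SD 0.5), rounded and limited to 1-5, with 200,000 pairs per setting. The pairs (d, b) = (0.3, 0), (0, 0.3), (0.15, 0.15) and (−0.2, 0.5) gave means of 0.276 to 0.279 and SDs of 0.776 to 0.781. With both at zero the mean was 0.003. Because d and b enter only as a sum, the agreement is by construction. It illustrates the point and does not measure the shift.

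**The case against.** The strongest reply is that this is a declared open-label, exploratory study whose aims include expert opinion for the manufacturer, with no test, margin or efficacy decision. That stands as a limit on the consequence. It does not settle the reading: the open-label statements concern imaging procedures, and stored images can still be graded with labels hidden.

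A second reply is that protocol 7.2 already commits to noise and SNR, and that the Precis and section 2 allow paired comparisons. This also stands. A reader might infer that these measurements have been dropped, but nothing in the SAP withdraws them. The gap is that the SAP does not name them as outcomes. Nor would they show how much of a grade difference is due to the reader, since the grade also covers contrast, artefacts and post-processing.

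A third reply is that checks exist. The principal investigator reviews the data, and section 2 says measurements are recorded for review. A reader might conclude from protocol 8.1 that nobody looks at the readings again, but the text supports only the absence of monitoring and independent audit of image interpretation. None of these checks is described in a way that would reveal expectation bias.

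Finally, image texture may disclose the detector even when labels are hidden, and coded grading may change the method if side-by-side relative grading was intended. Both are real limits on the benefit of the remedy.

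**Conclusion.** The point holds conditionally. If readings are unmasked, an expectation shift of unknown size and direction adds to the reported mean difference, and the planned mean and SD cannot separate it from a detector effect. The figures of 0.10 to 0.30, or 0.05 to 0.30 with the scale limit, rest wholly on assumed shares and show non-separability only.

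Three stronger readings are tempting but unsupported. One is that readers were in fact unmasked: the documents are silent, which does not establish it. Another is that using a rating departs from the protocol: sections 2 and 7.2 list radiologist ratings alongside the objective measures. The third is that error rates are inflated or PCCT is favoured: no test is planned, and the documents' expectations point both ways.

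What remains is a possibly biased descriptive estimate that should be better protected because doing so is cheap. Confidence is moderate, since actual reading practice is not stated.

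**What to change.** Add to SAP 6.1:

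> The same readers grade both series of each patient on the existing 5-point scale, with detector and series labels hidden, under a random code and in random order, limited to the common volume where feasible. Cases already graded unmasked are reported separately and need not be re-read. Image texture may still reveal the detector; this is a limitation.

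The common-volume clause matters because PCCT often covers less, and a difference in coverage could itself identify the series.

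Name the paired noise and SNR differences in the common volume as SAP secondary outcomes, citing protocol 7.2. They are reader-independent supporting evidence and should not be presented as apportioning the grade difference.

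**Cost.** SAP wording and image preparation for up to 750 pairs, with the same readers, stored images and scale and no extra scans. The code number in protocol 6.2 identifies images in the research database without naming the patient. It does not hide the detector, so a reading code is still needed.

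**Downsides.** Preparation time, some departure from ordinary reading conditions and from side-by-side grading if that was intended, separate reporting of earlier unmasked cases, and limited benefit where texture reveals the detector.

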7.0 Missing data

If PCCT data is incomplete, or not performed, the data will not be included.
